Tranexamic acid to Reduce Infection after Gastrointestinal Surgery: the TRIGS Trial

2. Trial registration

Prospectively registered (ClinicalTrials.gov identifier NCT04192435)

3. SAP version

Version: 1.0 Date: 07/11/2025

4. Protocol Version

This document has been written based on information contained in the TRIGS study protocol Version 1.4 dated 30 June 2022.

5. SAP Revisions

This SAP provides additional details and clarifies analysis approaches outlined in the TRIGS study protocol.

6. Names and affiliations

Document prepared by [name], Monash University; and [name], Alfred Hospital

[name]

Signatures:

Signature of senior statistician responsible ([name]):

Date: 13/11/2025

Date: 13/11/2025

Signature of chief investigator ([name]):

3

7. Brief background and rationale

Refer to the protocol for a detailed background to this trial, version 1.4, dated 30 June 2022.

8. Objectives

Research hypothesis:

We hypothesise that among adult patients schedule for elective or semi-elective open or lap-assisted gastrointestinal surgery (oesophageal, gastric, hepatobiliary, pancreatic, colorectal) with one or more risk factors for complications that a bolus of study drug (0.15 ml/kg TxA 15mg/kg before surgical incision, and then infusion at 0.05 ml/kg/h until end of surgery) will reduce the incidence of surgical site infection compared to matched placebo.

Study objective:

Primary objective: To determine whether TxA, compared to matched placebo, decreases the risk of surgical site infection

SAP version: Version: 1.0 Date: 13/11/2025

Section 3: Trial Methods

9. Trial design

International, multicentre, pragmatic, double-blind, placebo-controlled randomised clinical trial.

10. Randomisation

Patients will be randomly assigned using permuted blocks of sizes 6 to 12 from a computer-generated list to either receive IV TxA or placebo on the day of surgery, but after confirmation of scheduling. Random assignment will be done using a computer-generated code, accessed via a web-based service. Group assignment will be stratified by site and diabetes status.

11. Sample size

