Blood transfusion reactions	Binary outcome: any incidence of transfusion reaction	Binary variable 0 = no transfusion reaction; 1 = transfusion reaction	Any blood transfusion reaction following any blood product transfusion

24. Analysis methods

Analysis of primary outcome, and binary secondary/safety outcomes:

For the primary analysis of binary outcomes, we will use log-binomial models adjusting for the stratification variable of diabetes, with random effects for the stratifying variable of site. If that model fails to converge, a log-binomial model with the same link function and adjusting for the stratification variable of diabetes but with cluster-robust standard errors instead of random effects for site. Results will be expressed as risk ratios with 95% confidence intervals.

For analyses based on multiply imputed datasets: if a model fails to converge for more than one quarter of imputed datasets, the model with cluster-robust standard errors will instead be fit.

Days at home up to 30 days after surgery

DAH30 will be compared between groups using median regression adjusting for the stratification variable of diabetes, with cluster robust standard errors for site. DAH-30 is calculated using mortality and hospitalisation data from the date of the index surgery (= Day 0). For example, if a patient died on day 2 after their surgery whilst still an inpatient, they would be assigned zero (0) days at home; if a patient was discharged from hospital on Day 6 after surgery but was subsequently re-admitted for 4 days before their second hospital discharge, then they would be assigned a DAH-30 value of 20. If a patient has complications and spends 16 days in hospital, and then is transferred to a nursing facility for rehabilitation, and spend 24 days there before finally being discharged to their own home, they would be assigned a DAH-30 value of zero (0), even though 30-16-

24 = -10 because the minimum value of DAH-30 should be zero. If a patient dies within 30 days of surgery, irrespective of whether they have spent some time at home, DAH-30 will be scored as zero (0).

In addition to presenting a difference in medians between groups with respect to DAH-30, a difference in lower quartiles (i.e. 25th percentiles) will be presented.

Peak C Reactive protein and volume of red blood cell transfusion

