These outcomes will be compared between groups using mixed effects linear regression models adjusting for the stratification variable of diabetes, with random effects for the stratifying variable of site.

25. Statistical Methods – adjustment for covariates

Supplementary analyses for the primary outcome and the secondary outcome of any red cell transfusion will adjust for any prognostic variables imbalanced at baseline.

For the primary outcome, variables with apparent imbalance out of the following list will be adjusted for:

- Patient age
- ASA physical status
- Diabetes
- Current smoker
- Oral steroid
- Open surgery

For the outcome of any red cell transfusion, variables with apparent imbalance out of the following list will be adjusted for:

- Patient age
- ASA physical status
- Body mass index (weight/height²)
- Chronic renal disease
- Aspirin
- Preoperative haemoglobin
- Open surgery

26. Statistical Methods – subgroup analyses

Subgroup analyses of the primary outcome and any red cell transfusion will be conducted for the following subgroups:

- i) Age strata (\leq 60 yr; 61–70 yr;71–75 yr;>75 yr);
- ii) Patient sex;
- iii) BMI strata (≤ 18.5 ; $\geq 18.5-25.0$; $\geq 25.0-30.0$; $\geq 30.0-35.0$; ≥ 35.0);
- iv) ASA physical status
- v) Diabetes status (i.e. the stratification variable);
- vi) Country;
- vii) Type of GI surgery;
- viii) Duration of surgery (approximate quartiles)

Models for these analyses will be as described in Section 27 for the primary analysis, including terms for the subgroup indicator and interactions between the subgroup and randomised group. Treatment effects in each subgroup will be reported.

27. Missing data reporting and assumptions/statistical methods to handle missing data

Multiple imputation of outcomes will be undertaken if the proportion of missingness of the primary outcome

is >5%.

Missing baseline characteristics will be imputed using single mean imputation. Baseline characteristics of participants who did and did not provide the primary outcome will be compared, and will be used to inform multiple imputation models. T-tests or Wilcoxon rank-sum tests will be used to compare continuous characteristics (depending on whether these had approximately symmetric distributions or not); chi-squared tests will compare categorical characteristics between participants with and without the primary outcome.

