Missing outcome values will be imputed separately by treatment group. Imputation models will include treatment group, diabetes status, and baseline characteristics that appear to be different between participants who provided complete follow up data and participants who did not. Imputation models for continuous outcomes will also include terms for site. Imputation models for binary outcomes will not include terms for site due to the possibility of perfect prediction in small sites.

Initially, imputation via chained equations will be attempted for outcomes, with separate imputation for each outcome if this imputation fails. Binary outcomes will be imputed using logistic regression models, and continuous outcomes imputed via with predictive mean matching from the 5 nearest neighbours. Imputed datasets will be compared to complete data using density plots for continuous outcomes and plots of proportions for binary outcomes.

28. Additional Analyses

As-treated and per protocol analyses of the primary outcome and any red cell transfusion will also be conducted. As noted in the E9(R1) addendum, these additional analyses may be subject to severe bias and may not correspond to a relevant estimand.

Data collected prior to the trial re-start (the "contamination dataset") will also be considered. A table summarizing the baseline characteristics of patients by randomised treatment group will be presented. The primary outcome, red cell transfusion outcomes, and healthcare associated infections will be analysed as described above in this dataset.

29. Harms

Safety outcomes and adverse events will be reported by treatment group.

30. Statistical Software and code

Stata v19 or later will be used (StataCorp. Stata Statistical Software: Release 19. College Station, TX: StataCorp LLC); or R v 4.4.1 or later. Any user-written R packages used will be referenced.

The following code will be applied for the analysis of primary and secondary outcomes:

Primary outcome and binary secondary outcomes:

```
xi: gllamm outcome i.TreatmentGroup i.diabetes, i(site) fam(binomial)
link(log)
```

Primary outcome and binary secondary outcome backup code:

```
binreg outcome i.TreatmentGroup i.diabetes, rr cluster(site)
```

DAH30:

```
qreg2 outcome i.TreatmentGroup i.diabetes, cluster(site)
qreg2 outcome i.TreatmentGroup i.diabetes, cluster(site)
```

Continuous outcomes:

mixed outcome i.TreatmentGroup i.diabetes || site: , reml

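### If the site-clustered fallback is used for the Country subgroup, confidence intervals and p-values will be too optimistic for any country with few sites

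*SAP*

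**What the plan says.** - **Model.** For binary outcomes, SAP Section 24 states "we will use log-binomial models adjusting for the stratification variable of diabetes, with random effects for the stratifying variable of site".
- **Fallback.** On non-convergence, Section 24 keeps the log link and the diabetes adjustment, "but with cluster-robust standard errors instead of random effects for site". For imputed data, "if a model fails to converge for more than one quarter of imputed datasets, the model with cluster-robust standard errors will instead be fit".
- **Code.** Section 30 gives the backup command as "binreg outcome i.TreatmentGroup i.diabetes, rr cluster(site" (closing bracket omitted here). No small-sample correction is mentioned.
- **Subgroups.** Section 26 covers SSI and any red cell transfusion and lists Country among eight factors. It says: "Models for these analyses will be as described in Section 27 for the primary analysis, including terms for the subgroup indicator and interactions". It adds: "Treatment effects in each subgroup will be reported". Section 27 is the missing-data section. The primary model and its fallback are described in Section 24.
- **Design.** Section 9 describes the trial as "International, multicentre, pragmatic, double-blind, placebo-controlled randomised clinical trial". Section 10 has patients randomised individually, with stratification by site and diabetes.
- **Not in the SAP.** There is no number of sites per country, no minimum number of sites, no pooling of small countries and no separate fallback for Country.

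**The concern.** A cluster-robust variance needs a reasonable number of clusters behind the parameter of interest. For a whole-trial effect those clusters are all the sites. For a country-specific effect they are, in practice, only that country's sites. Age, sex, BMI, ASA status and diabetes all vary within sites, so Country is the listed factor in which whole sites fall inside a single level by construction.

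If the fallback is triggered, a country with two to five sites could show a plausible-looking but much too narrow interval. A chance difference in SSI or transfusion could then be reported as a benefit or harm specific to that country. Section 15 plans no multiplicity adjustment that would temper it. Replacing the standard error once results are known would be a post-hoc change.

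**Working it through.** **1. The plan's own figure.** The SAP gives no figure for the Country analysis, so the nearest check is the sample size in Section 11. With p1 = 0.12, p2 = 0.084, mean 0.102, two-sided 5% and 90% power:

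n = [1.960·√(2·0.102·0.898) + 1.2816·√(0.12·0.88 + 0.084·0.916)]² / 0.036² = (0.8389 + 0.5475)² / 0.001296 ≈ 1,483.2, which rounds up to the stated 1,484 per group.

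The event rate and planned enrolment are therefore safe inputs.

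**2. Why the standard error shrinks.** With a log link, patient i contributes x_i·(y_i − μ_i)/(1 − μ_i) to the score. Once country and country-by-treatment terms are in the model, the fitted scores for a country's intercept and treatment effect sum to zero over that country's patients.

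- *One site:* that sum is the site's own cluster total. The country's contribution to the sandwich variance vanishes, apart from a trace through the shared diabetes coefficient.
- *m sites:* the m cluster totals are constrained to sum to zero, so only about m − 1 are free. The usual correction G/(G − 1) uses all G sites in the trial, not m.

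**3. Approximate size by formula.** For m similar sites the squared standard error behaves like σ²·(χ² with m − 1 df)/m·G/(G − 1). The test then rejects when |t with m − 1 df| > 1.96·√[((m − 1)/m)·G/(G − 1)]. Assume 40 sites elsewhere, so G = 40 + m:

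| m | Critical value | Approximate false-positive rate |
|---|---|---|
| 2 | 1.96·√(0.5·42/41) = 1.403 | 39% |
| 3 | 1.96·√(0.667·43/42) = 1.619 | 25% |
| 5 | 1.96·√(0.8·45/44) = 1.773 | 15% |
| 8 | 1.96·√(0.875·48/47) = 1.853 | 11% |
| 15 | 1.96·√(0.933·55/54) = 1.911 | 8% |

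**4. Simulation with no treatment effect anywhere.**

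- *From the SAP:* 3,300 patients, SSI about 12%, 30% diabetic, allocation stratified by site and diabetes, two-sided 5%.
- *Assumed:* 40 sites in the rest of the trial, 80 to 200 patients per small-country site, between-site SD 0.3 on the log-risk scale, diabetes RR 1.3.
- *Fit:* log-binomial with treatment, country, country-by-treatment and diabetes; sandwich variance clustered on site with factor G/(G − 1); z = 1.96; 600 trials per row.

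| Sites × patients | Mean clustered SE | True SD of log RR | Ratio | False positives, clustered | False positives, model-based |
|---|---|---|---|---|---|
| 1 × 200 | 0.0006 | 0.449 | 0.001 | 98.7% | 4.0% |
| 2 × 100 | 0.237 | 0.420 | 0.57 | 37.5% | 4.0% |
| 3 × 100 | 0.233 | 0.330 | 0.71 | 25.2% | 4.8% |
| 5 × 80 | 0.237 | 0.285 | 0.83 | 17.0% | 5.7% |
| 10 × 80 | 0.182 | 0.202 | 0.90 | 10.0% | 5.3% |
| 20 × 80 | 0.131 | 0.140 | 0.93 | 9.2% | 5.5% |

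Further null simulations under comparable assumptions (for example 30 sites elsewhere and 100 to 150 patients per small-country site) gave 36% to 40% with 2 sites, 23% to 26% with 3, 15% to 18% with 5, 10% to 12% with 8 and 7% to 9% with 15. At 8 sites the median clustered SE was 0.170 against a model-based 0.193, which is 12% low. With between-site SD set to zero the rates for 2, 3, 5, 8 and 15 sites were 40%, 25%, 15%, 10% and 6%, so the result does not depend on the assumed heterogeneity.

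**The case against.** **It is conditional.** The mixed model must fail, the fallback must carry over to subgroups, and some country must have few sites and be reported alone. This stands for the first and third conditions: the SAP settles neither. The protocol's subgroup section, which Section 31 cites as the source of the list, is not at hand and might group countries. The second condition is an inference, but a firm one. Section 27 contains no primary-analysis model, so Section 24 is the only sensible target of the cross-reference.

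**The one-site case would be noticed.** Agreed. An interval of almost no width is visibly degenerate. The harder case is two to five sites, where the interval looks ordinary.

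**The consequence is limited.** Also agreed. Country is one of eight subgroup factors, on a back-up path.

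**Stronger readings the SAP does not support.** A reader might infer:

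- *That the country-specific RR is biased.* It is not; only the interval and p-value are wrong.
- *That a country-by-treatment test will be falsely positive.* Section 26 includes interaction terms and promises effects in each subgroup, but does not explicitly promise a formal interaction test.
- *That everything up to eight sites is badly wrong.* At eight sites the standard error is about 11% to 12% low, which is moderate.
- *That the whole-trial fallback fails in the same way.* It draws on every site and is not the subject of this point. Individual randomisation does mean that clustering is not strictly needed there either, but that does not create the few-cluster problem shown here.

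**Conclusion.** The point holds in conditional form. If the random-effects model does not converge in the Country analysis, the stated fallback gives country-specific intervals that are too narrow and p-values that are too small wherever a country has few sites. The error is serious at 2 or 3 sites (false-positive rates of roughly 23% to 40%), clear at 5 (15% to 18%), moderate at 8 (10% to 12%) and small by 15 (7% to 9%).

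The mechanism is algebraic, and the formula and the simulations agree. The sizes rest on assumed numbers of sites and patients per country. Whether any country is that small, and whether the fallback will be needed, cannot be told from the SAP. The SAP does provide for non-convergence in two places, and the extra country terms plausibly make it more likely. The primary result is untouched.

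**What to change.** In Section 26, correct the cross-reference from Section 27 to Section 24. In Sections 24 and 26, state that if the random-effects model does not converge for the Country subgroup, the fallback is one of the following:

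- the same log-binomial model (treatment, diabetes, country, country-by-treatment) with model-based, non-clustered standard errors; or
- a Mantel-Haenszel risk ratio stratified by site within each country, which needs no iterative fit and so also serves if the log-binomial model itself fails.

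Either is valid because patients are randomised individually within site. In the simulations, model-based standard errors brought false positives to between about 2% and 6%. The whole-trial fallback can stay as written.

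The cost is one or two sentences and one line of code, with no new data. The downsides are small: the Country fallback then differs from the main one, and its interval is slightly conservative when baseline risk differs between sites.

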patients included in their randomized groups (treatment policy strategy) - Death prior to identification of SSI within the relevant window: if a patient dies prior to the identification of an SSI, their outcome will be "no SSI" ("while alive" strategy)	set have a missing primary outcome. Results of a complete case analysis will also be provided. Supplementary analysis: The analysis of the primary outcome will be repeated in As-treated and Per Protocol analysis sets.		

The relative risk

will

Population-level summary measure: Relative risk | Analysis approach:

of SSI if treated with TxA compared with no TxA.	estimated using a log-binomial model adjusted for the
	stratification variable of diabetes, with random effects
	for the stratifying variable of site.

Section 5: Trial Population

18. Screening Data

Screening data will be collected and a CONSORT flow diagram will be used to summarise this data.

19. Eligibility

Trial inclusion criteria are described in the trial protocol. Reasons for exclusion will be summarised in the CONSORT flow diagram.

20. Recruitment

A CONSORT flow diagram will be used to describe the number of people consented to participate, randomised, allocated to each treatment group, those lost to follow up (including reasons) and analysed.

21. Withdrawal/follow-up

All participants who are enrolled and randomly assigned to a group, and undergo surgery, must be followed for the duration of the study (unless they withdraw consent) even if they are withdrawn from the active phase of the trial. Losses to follow-up (including reasons) will be summarised in the CONSORT flow diagram by treatment group.

22. Baseline descriptive measures

Baseline characteristics will be summarised as appropriate (means and standard deviations for continuous variables that appear to be distributed approximately symmetrically, medians and interquartile ranges for other continuous variables, counts and percentages for categorical variables). Tests of statistical significance will not be undertaken for comparing baseline characteristics of treatment groups; rather the clinical importance of any imbalance will be noted.

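### SAP Section 25 lets a prognostic covariate into the supplementary adjusted analyses only if it looks imbalanced, so the covariate set rests on post-hoc judgement and most of the available precision is lost.

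*SAP*

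**What the plan says.** Section 25 of the SAP sets the general rule: "Supplementary analyses for the primary outcome and the secondary outcome of any red cell transfusion will adjust for any prognostic variables imbalanced at baseline".

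It then applies the rule to each outcome:
- SSI: "For the primary outcome, variables with apparent imbalance out of the following list will be adjusted for". The list has six variables: age, ASA status, diabetes, current smoking, oral steroid and open surgery.
- Transfusion: "For the outcome of any red cell transfusion, variables with apparent imbalance out of the following list will be adjusted for". The list has seven variables: age, ASA status, BMI, chronic renal disease, aspirin, preoperative haemoglobin and open surgery.

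The only guidance on judging imbalance is in Section 22: "Tests of statistical significance will not be undertaken for comparing baseline characteristics of treatment groups; rather the clinical importance of any imbalance will be noted".

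The main models are fixed in advance. Section 24 says: "For the primary analysis of binary outcomes, we will use log-binomial models adjusting for the stratification variable of diabetes, with random effects" for site. Section 10 says: "Group assignment will be stratified by site and diabetes status". Section 30 gives code for the main models and none for the supplementary adjusted ones.

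**The concern.** A covariate improves precision because it predicts the outcome, not because it happens to differ between arms. The SAP has already named the variables that it regards as prognostic. Filtering those lists by observed imbalance adds discretion and leaves out useful predictors in most realisations of the trial.

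The filter is also undefined. Section 25 gives no metric, no threshold, no decision-maker and no statement that the choice is made blind to outcome. Two competent statisticians could fit different models and report different adjusted relative risks. If no variable is judged imbalanced, the supplementary analysis merely repeats the main one.

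The diabetes entry is a separate inconsistency. It is a stratification factor, so it will be close to balanced by design, and it is already in every main binary model. Read literally, Section 25 leaves unclear whether the supplementary SSI model keeps it.

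**Working it through.** **Inputs from SAP Sections 11 and 14.** Control rate 12%, relative risk 0.7 (8.4%), two-sided 5%, 1,484 per group for 90% power, planned enrolment 3,300, transfusion in 12% of patients. Equal arms of 1,650 are assumed.

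**The plan's own figure.** With pooled variance and mean rate 0.102:

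n = [1.960·√(2·0.102·0.898) + 1.282·√(0.12·0.88 + 0.084·0.916)]² / 0.036² = 1,484 per group.

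This matches. Power for 14% versus 9.8% with 1,484 per group is 94.3%, which also matches. With 1,650 per arm, power for 12% versus 8.4% is 92.8%.

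**Chance of a covariate being selected.** Under simple randomisation a standardised mean difference (SMD) has mean 0 and SE 2/√3300 = 0.035. The median absolute SMD is 0.6745 × 0.0348 = 0.023. The last column is (1 − p)⁵ for the five SSI covariates other than diabetes, taken as independent.

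| Assumed cut-off | A given covariate enters | None of the five SSI covariates enters |
|---|---|---|
| SMD above 0.10 | 0.4% | 98% |
| p<0.05 | 5% | 77% |
| SMD above 0.05 | 15% | 44% |
| p<0.20 | 20% | 33% |

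For the seven transfusion covariates, the chance that none enters is 0.95⁷ = 70% at p<0.05 and 0.80⁷ = 21% at p<0.20. Haemoglobin is left out in 80% to 99.6% of trials across these cut-offs. The p-value rows only calibrate the size of a difference, since Section 22 excludes such tests.

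**Precision forgone, transfusion, relative risk 0.7.** The documents give no haemoglobin effect, so two are assumed.
- Log relative risk −0.9 per SD (steep): in simulation the SE of the log relative risk falls from 0.106 to 0.100, by 0.006/0.106 = 6%. With |ln 0.7| = 0.357, power goes from Φ(0.357/0.106 − 1.96) = 92.0% to Φ(0.357/0.100 − 1.96) = 94.6%, a gain of about 3 points.
- Log relative risk −0.5 per SD: the SE falls by about 1.5%, to 0.106 × 0.985 = 0.1044. Power becomes Φ(0.357/0.1044 − 1.96) = 92.7%, a gain of about 1 point.

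**Effect of the selection rule.** A separate simulation used 3,000 trials per scenario, a logistic model, an assumed relative risk of 0.75 and one covariate standing in for haemoglobin.

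| Assumed odds ratio per SD | Never adjusted | Only if p<0.05 | Only if p<0.20 | Always adjusted |
|---|---|---|---|---|
| 0.6 | 81.4% | 81.6% | 82.0% | 82.4% |
| 0.4 | 80.7% | 81.1% | 81.4% | 83.6% |
| 0.3 | 80.1% | 80.7% | 81.8% | 85.2% |

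At odds ratios 0.4 and 0.3, selection loses most of the gain under either cut-off. At 0.6 the whole gain is only about 1 point, close to the Monte Carlo error of one estimate (√(0.81 × 0.19/3000) = 0.7 points). Type I error was 4.0% to 5.0% under every rule.

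**The case against.** The strongest reply is about scope. Section 25 governs supplementary analyses of two outcomes only, and the candidates are closed lists fixed in advance. The models on which SSI and transfusion will be judged contain diabetes and site whatever the baseline table shows. An analysis meant to check for chance imbalance has nothing to add when the arms are balanced. All of this stands and limits the size of the point. It does not defend the rule, because such a check still needs a criterion, and adjusting for the full list serves the same purpose without one.

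Second, the power gain does not reach the main transfusion analysis, which omits haemoglobin under either rule. That is right: the gain belongs to the supplementary analysis. Haemoglobin's strength is also assumed, since the SAP calls the variables prognostic without quantifying them. No precision loss was calculated for SSI.

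Third, the two harms pull against each other. Under a strict cut-off the adjusted model usually equals the main one and analysts rarely differ. Under a loose one covariates enter more often and discretion matters more. This is fair. Because the SAP states no cut-off, a reader cannot tell which applies.

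A reader might infer that the primary result is compromised or its false-positive rate inflated. The documents do not support this: the primary model is fixed, and the simulations show no inflation under fixed cut-offs. An unstated cut-off chosen with outcomes in view was not simulated. A reader might also infer that the adjusted SSI analysis will nearly always equal the primary one. That holds only under the stricter assumed cut-offs; at an SMD of 0.05 it would do so 44% of the time.

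**Conclusion.** The point holds for the supplementary adjusted analyses of SSI and any red cell transfusion, and only there. The covariate set depends on an undefined judgement about the observed arms, and a given prognostic variable would enter in about 0.4% to 20% of trials under the cut-offs considered. For transfusion the cost is about 1.5% to 6% in standard error, roughly 1 to 3 power points at a relative risk of 0.7. The other simulation, at a relative risk of 0.75, gives about 1 to 5 points.

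These figures rest on equal arms, simple randomisation, the assumed cut-offs and an assumed haemoglobin effect. The figures for several covariates also assume independence, although age and ASA status may well be correlated. Listing diabetes as conditional is a small inconsistency, harmless if the supplementary models retain it. This is a modest flaw that should be corrected because the better rule needs no new information.

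**What to change.** Replace the selection rule in Section 25 with wording such as:

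> The supplementary adjusted analyses will include all listed covariates regardless of observed imbalance, in addition to diabetes and site.

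Enter age, BMI and haemoglobin as continuous terms and say so. Remove diabetes from the conditional SSI list, since the models contain it anyway.

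Add a convergence rule for these models. The fallback in Sections 24 and 30 is still log-binomial, and continuous covariates make that model harder to fit. If it does not converge, use Poisson regression with robust standard errors clustered by site, so that the handling of site in Section 24 is kept.

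The cost is SAP wording and a line of code, because every variable is already listed. The downside is a few more parameters and a higher chance of log-binomial non-convergence, which the added Poisson fallback handles.
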